Smartphone-based CBT for OCD can address gaps in access to treatment, offering standardized, high-quality, empirically-based interventions in a low-cost and accessible format. Additionally, given the low rate of doctoral-level clinicians specializing in CBT for OCD treatment, it would be advantageous to establish whether mobile app-based CBT can be administered effectively with assistance from trained bachelors-level coaches who are supervised weekly by licensed, doctoral-level psychologists. This would greatly enhance scalability of the treatment.

II. SPECIFIC AIMS

The overarching purpose of this project is to test the feasibility, acceptability, and efficacy of mobile-app-delivered CBT for OCD. We accomplish this through Specific and Exploratory Aims 1-3.

Specific Aim 1: In a well-powered, randomized-controlled trial, we will test the efficacy of the active treatment arm (Perspectives OCD) compared to a supportive attentional control (HealthWatch) in reducing primary (i.e., OCD symptom severity, measured via Y-BOCS) and secondary outcomes (e.g., quality of life, depression, social and occupational functioning) at week 12.

Primary Hypothesis: We hypothesize that participants receiving app-based CBT for OCD will have greater improvement in Y-BOCS scores than those in the supportive attentional control condition at treatment endpoint (week 12).

Secondary Hypothesis: We hypothesize that participants receiving app-based CBT for OCD will have greater improvement on secondary clinical outcome measures (i.e., depression (QIDS-SR), functional impairment (WSAS), and quality of life (Q-LES-Q)) than those in the supportive attentional control condition at treatment endpoint (week 12).

Exploratory Aim 2: Feasibility and Acceptability

Hypothesis: We hypothesize that app-delivered CBT for OCD will be feasible (based on drop-out rates) and acceptable (based on descriptive statistics of patient satisfaction, app use, and app feedback as well as qualitative feedback) to individuals with OCD.

Exploratory Aim 3: Maintenance of gains (Y-BOCS, QIDS-SR, Q-LES-Q-SF, WSAS) at follow-up (week 24).

Hypothesis: There will be no significant difference between the primary and secondary outcomes measured at treatment endpoint (week 12) and end of follow-up (week 24) in the group that participated in the app-CBT condition.

III. SUBJECT SELECTION

Overview:

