Primary endpoint: Difference in OCD severity (Y-BOCS) at the end of treatment (i.e., week 12 assessment).

Hypothesis 1: Participants receiving app-CBT will have lower Y-BOCS scores than those in the supportive attentional control condition at treatment endpoint (week 12).

Secondary endpoints: Difference in secondary clinical outcomes at the end of treatment (i.e., week 12 assessment)

Hypothesis 2: Participants who receive the app-CBT will have better scores on secondary clinical outcome measures than those in the supportive attentional control condition at treatment endpoint (week 12) with respect to:

H2.1: depression severity, as measured by the QIDS-SR, where lower scores are better.

H2.2: functional impairment, as measured by the WSAS, where lower scores are better.

H2.3: quality of life, as measured by the Q-LES-Q-SF, where higher scores are better.

Exploratory endpoint 1: Feasibility and Acceptability

Hypothesis 3.1: Drop-out from app-delivered CBT for OCD will not be higher than drop-out from the supportive attentional control condition, which will indicate feasibility.

Hypothesis 3.2: Patient satisfaction ratings (i.e., CSQ total scores) in the group receiving app-delivered CBT for OCD will not be lower than those in the supportive attentional control condition, which will indicate acceptability.

Hypothesis 3.3: App-delivered CBT for OCD will be acceptable to individuals with OCD based on descriptive statistics of app use, app feedback, and qualitative feedback comments.

Exploratory endpoint 2: Maintenance of gains (Y-BOCS, QIDS-SR, WSAS, Q-LES-Q-SF) during follow-up (at 3-month and 12-month follow-up assessments).

Hypothesis 4: At the 12-month follow-up assessment, participants who received app-CBT will have lower Y-BOCS scores than those in the supportive attentional control condition.

Exploratory endpoint 3: Treatment utilization for OCD concerns following the 3-month follow-up.

Hypothesis 5: Participants assigned to the app-CBT treatment condition will be less likely to seek additional treatment for OCD than participants assigned to the supportive attentional control condition prior to the 12-month follow-up assessment.

C. Statistical methods

For all statistical analyses, we will use a Type I error probability of 0.05 to determine significance unless otherwise noted.

Primary endpoint: Difference in OCD severity (Y-BOCS) at the end of treatment (i.e., preliminary efficacy for primary OCD symptoms)

Analysis:

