- H3.2: We will analyze patient satisfaction, as measured by on Client Satisfaction Questionnaire (CSQ) in a hierarchical mixed model (i.e., GLMM) that will include time (categorical; week 6 and week 12), treatment (app-CBT vs. supportive attentional control), and their interaction as fixed effects, and will model time as a repeated measure using a compound symmetry covariance structure. We will test group differences with one-tailed tests in patient satisfaction (testing for lower satisfaction) at both week 6 and week 12 using specific contrasts with $\alpha=.025$ to adjust for multiple testing. Non-significant results of these tests will be interpreted as indications of treatment acceptability, while lower satisfaction will be interpreted as indicating a lack of acceptability.
- H3.3: Quantitative (i.e., app feedback questionnaires, uMARS) and qualitative participant feedback about app features will be summarized for the app-CBT group using descriptive statistics.

Exploratory endpoint 2: Maintenance of gains (Y-BOCS, QIDS-SR, WSAS, Q-LES-Q-SF) at follow-up (week 24).

Analysis:

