We will use hierarchical mixed models similar to the ones used for the primary and secondary outcome analyses, but will add follow-up assessments (i.e., 3-month and 12-month) to the data as additional time-points. We will then use specific contrasts (for each outcome model) to test for significant treatment group differences at the 12-month follow-up time-point. In the case that at least 10% of the participants who completed the end-of-treatment assessment initiated additional or subsequent evidence-based treatment for OCD at clinically relevant dosage (for medication) or frequency (for therapy), we will conduct a sensitivity analysis for this aim using treatment (yes/no) as a time-varying covariate in the model to account for the potential effect of outside treatment. In this context, ‘evidence-based’ treatments will be operationally defined to include any psychosocial or medication treatments indicated for OCD or closely related anxiety disorders that have shown efficacy in prior clinical trials, and ‘clinically relevant dosage’ will be evaluated by psychiatrists or psychologists in our treatment program who specialize in OCD or related disorders. In addition, we will also add descriptive stats about how many participants are responders at both end-of-treatment and 12-month follow-up, how many participants are new responders by the 12-month follow-up, how many participants are no longer considered responders at the 12-month follow-up, and how many participants were not considered responders at either assessment. No formal comparisons will be made between treatments in these numbers.

Exploratory endpoint 3: Treatment utilization for OCD concerns following the 3-month follow-up.

Analysis:

We will use logistic regression analysis to examine whether the likelihood of seeking further treatment for OCD during the treatment or follow-up phases (overall, combined) differs between participants who were assigned to the app-CBT and those assigned to the supportive attentional control condition. For this analysis, we will operationally define “treatment utilization” as any indication of participants seeking treatment for OCD during or following the treatment phase, regardless of whether the treatments sought are pharmacological or therapy-based, at sufficient or insufficient dosage/frequency, or considered evidence-based or not.

D. Power analysis

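### Exploratory Aim 3 asks whether app-arm gains hold from week 12 to week 24, but the follow-up analysis names only between-arm contrasts at 12 months, so no named contrast answers it.

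*Combined protocol and SAP*

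**What the plan says.** Four places describe maintenance of gains, and they do not match.

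- **Section II, Exploratory Aim 3.** The hypothesis is: "There will be no significant difference between the primary and secondary outcomes measured at treatment endpoint (week 12) and end of follow-up (week 24"). The comparison is confined to one arm, since the sentence limits it to outcomes "in the group that participated in the app-CBT condition". This is one arm, one interval and four outcomes (Y-BOCS, QIDS-SR, Q-LES-Q-SF, WSAS).
- **Section VI.B, Exploratory endpoint 2.** Maintenance on the same four outcomes is placed "during follow-up (at 3-month and 12-month follow-up assessments"). The only hypothesis beneath it, Hypothesis 4, is: "At the 12-month follow-up assessment, participants who received app-CBT will have lower Y-BOCS scores than those in the supportive attentional control condition".
- **Section VI.C, heading of the analysis.** "Exploratory endpoint 2: Maintenance of gains (Y-BOCS, QIDS-SR, WSAS, Q-LES-Q-SF) at follow-up (week 24").
- **Section VI.C, text of the analysis.** The models "add follow-up assessments (i.e., 3-month and 12-month) to the data as additional time-points". The contrasts, one per outcome model, then "test for significant treatment group differences at the 12-month follow-up time-point".

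Two supplements follow in the same text. If at least 10% of those who completed the end-of-treatment assessment start qualifying outside treatment, "we will conduct a sensitivity analysis for this aim using treatment (yes/no) as a time-varying covariate in the model". There are also descriptive counts of participants who stay, become, cease to be or never were responders between end of treatment and 12 months. The primary model in section VI.C stops at week 12.

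**The concern.** A difference between arms at 12 months is not a measure of whether the app arm kept its gains. It reflects what happens in both arms, so it can stay constant while gains are lost and shrink while they are kept. The plan itself gives reason to expect the second case. The footnote to the eligibility criteria (III.A) lifts the request to avoid outside treatment after the 3-month visit, and Hypothesis 5 predicts that controls will seek more OCD treatment than app-arm participants. The 3-month visit, taken here as week 24, is the last one at which that request still applies, and it has no contrast.

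At stake is an aim with a stated hypothesis and no named estimate. Because the sections disagree on comparison, time point and outcomes, a maintenance statement could be built on whichever version looks best once the data are in. The wording of Aim 3 adds a second problem: finding no significant change would not establish maintenance.

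**Working it through.** **1. Sections side by side**

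| Place | Comparison | Time | Outcomes |
|---|---|---|---|
| II, Aim 3 | within app arm | week 12 vs week 24 | four |
| VI.B, endpoint 2 | not stated | 3 and 12 months | four |
| VI.B, Hypothesis 4 | between arms | 12 months | Y-BOCS |
| VI.C, heading | not stated | week 24 | four |
| VI.C, contrasts | between arms | 12 months | four |

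Hypothesis 4 and the contrasts agree for the Y-BOCS. Nothing in the last row serves the first.

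**2. The plan's own figure**

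Section VI.D gives n = 116 from a difference of 0.76, SD 1.1, two-sided alpha 0.05, power 0.90 and 20% dropout. A two-sample t calculation needs 46 per arm (power 0.906). Then 46 / 0.80 = 57.5, rounded up to 58 per arm, or 116. The figure reproduces, but it concerns the week-12 between-arm contrast only. The plan gives no figure for Aim 3.

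**3. Does the planned contrast track maintenance?**

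Start from 0.76 at week 12 and assume a change of 0.3 on the same scale.

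- Both arms worsen by 0.3: the contrast stays at 0.76, although the app arm has lost 0.3.
- The app arm holds and controls improve by 0.3: 0.76 − 0.30 = 0.46, although the app arm has lost nothing.

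**4. Precision of the missing estimate**

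Inputs:

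- 120 randomized 1:1 gives 60 per arm.
- 60 × 0.80 = 48 at the plan's 20% dropout.
- 60 is the upper bound, since dropouts are asked to complete all assessments.
- 40 is an assumed further loss.
- The documents give no between-visit correlation ρ. Assumed: 0.5–0.8 for week 12 to 24, and 0.3–0.5 for week 12 to 12 months.

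Using a paired-t approximation to the model contrast, the 95% half-width in SD units is t(0.975, n−1) × √(2(1−ρ)/n).

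| n pairs | ρ = 0.3 | ρ = 0.5 | ρ = 0.8 |
|---|---|---|---|
| 40 | 0.378 | 0.320 | 0.202 |
| 48 | 0.344 | 0.290 | 0.184 |
| 60 | 0.306 | 0.258 | 0.163 |

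This gives about 0.16–0.32 SD for week 12 to 24, and 0.26–0.38 SD for week 12 to 12 months. To set these beside 0.76, multiply by the plan's SD of 1.1: about 0.18–0.35 and 0.28–0.42.

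**5. Why non-significance is weak evidence**

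With 48 pairs, SD 1.1 and ρ of 0.5 to 0.8, a two-sided 0.05 paired test has 34% to 68% power to detect a true worsening of 0.25 on the plan's scale (an assumed size). A real loss of that size would be missed in about a third to two thirds of trials, and Aim 3 would read each miss as support.

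**The case against.** The strongest reply is that the estimate is already latent in the plan. The follow-up model has categorical time by treatment and includes the 3-month visit, so the app-arm change from week 12 to week 24 is a linear combination of planned parameters. That stands, and it is why the remedy is cheap. But an estimate that can be formed is not one that has been specified.

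A second reply is that Aim 3 and the VI.C heading may simply predate the 12-month visit: Aim 3 calls week 24 the end of follow-up. If so, rewording them would suffice. The documents do not settle this. Even on that reading, VI.B still lists the 3-month visit and four outcomes under maintenance, and a between-arm contrast still does not measure maintenance.

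Third, the responder counts do describe persistence. They are prespecified, but they are descriptive, rest on the Y-BOCS alone and skip week 24. The sensitivity analysis may partly address outside treatment, but it is conditional and adds no within-arm or week-24 estimate.

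Fourth, Aim 3 strictly needs only the week 12 to 24 change, so adding the 12-month change goes further. That is fair as to Aim 3. The 12-month change is supported by VI.B, which places maintenance at both visits.

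Finally, the aim is exploratory. That limits the consequence but does not remove the gap.

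**Conclusion.** The concern holds. Followed exactly, the plan yields no named model contrast within the app arm and none at week 24, so Aim 3 goes unanswered although the data are collected and modelled. The contrast that is planned can read 0.76 when gains are lost and 0.46 when they are kept, given an assumed change of 0.3. The mismatch rests on the text alone. The precision figures are illustrative and depend on assumed correlations and pair counts. The point should be fixed, but it does not touch the primary or secondary analyses.

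**What to change.** Reconcile section II (Aim 3), VI.B (Exploratory endpoint 2 and Hypothesis 4), and the heading and text in VI.C on population, comparison, time point and outcomes. Suggested text for VI.C:

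> From the follow-up mixed model we will estimate, for each of the four outcomes, the app-CBT mean change with 95% CI (i) from week 12 to the 3-month visit (week 24) and (ii) from week 12 to the 12-month visit. Maintenance will be interpreted from these intervals and not from a non-significant p-value. If a maintenance claim is to be made, a margin will be fixed before any follow-up data are analysed. The 12-month between-arm contrast on the Y-BOCS tests Hypothesis 4; the same contrast on the QIDS-SR, WSAS and Q-LES-Q-SF is an additional exploratory contrast.

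Reword the Aim 3 hypothesis to match. A between-arm contrast at week 24 is optional. If the outside-treatment sensitivity analysis is applied to (i) or (ii), state that outside treatment is a post-randomisation covariate that may itself respond to worsening.

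The cost is wording plus two within-arm contrasts for each of four outcomes, eight in all, from a model already planned. No visits or data are added. The downside is a few more exploratory estimates, and intervals that may be inconclusive, more so at 12 months.

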The primary outcome model will be a hierarchical mixed model (i.e., GLMM) that will include time (categorical; baseline, mid-point, and end-of-treatment), treatment (app-CBT vs. supportive attentional control), and their interaction as fixed effects, and will model time as a repeated measure using either an autoregressive (AR1), Toeplitz, compound symmetry, or unstructured covariance matrix, based on best fit determined by AIC and BIC. The unstructured covariance matrix model will only be used if this model fits significantly better than alternative simpler models, based on -2 log likelihoods. The main hypothesis test will be based on a specific contrast of treatment difference at week 12. Because these analyses will include all subjects who are randomized and complete at least one assessment, it is an intent-to-treat analysis. These analyses will include only the 3 assessments from baseline to post-treatment and will not include the 3-month or 12-month follow-up (FU) assessments, because treatment response could be affected by subjects seeking other treatments during the FU period. Between-group effect sizes will be calculated using Cohen's *d*. This analysis will then be repeated using the per-protocol sample.

In addition to the analyses specified above, we will describe the proportion of subjects in each treatment arm who achieve response, where response is defined as a 25% or greater reduction in Y-BOCS score from baseline to end of treatment (week 12) (Storch et al., 2006). While no formal comparisons will be made between treatments, the reporting of response rates is clinically useful and will facilitate comparison to other studies in the field. We will report response as observed (excluding subjects with missing data at week 12) and will additionally examine how rates may change when a) applying a last observation carried forward approach, and b) conservatively considering subjects with missing week 12 scores as non-responders.

Secondary endpoint: Difference in secondary clinical outcomes (i.e., QIDS-SR, WSAS, Q-LES-Q-SF) at the end of treatment (i.e., preliminary efficacy for secondary symptoms)

Analysis:

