5. Participants' clinical improvement or deterioration will be assessed weekly via a participant-rated CGI-OCD collected via the app in the app-based CBT group or REDCap surveys in the supportive attentional control condition. Participants may be withdrawn from the study if their clinical condition deteriorates substantially. Deterioration will be defined by a rating of 6 (much worse) or 7 (very much worse) on the patient -rated CGI during three consecutive, weekly assessments and (2) PI judgment that remaining in the study is not in the participant's best interest. Of note, three consecutive weekly ratings of 6 or 7 on the weekly, participant-rated CGI-OCD will also trigger a notification to the clinician via text message or email. In the case that a BA-level coach is notified that a participant's CGI indicates deterioration, they will notify a doctoral-level clinician as soon as possible (and within 24 hours). A study clinician will follow up with a phone evaluation within 24 hours of the alert and refer the participant to a higher level of care if clinically indicated.
6. Ratings on a one-item self-report suicide questionnaire will be carefully monitored weekly via the app in the app-based CBT group or REDCap surveys in the supportive attentional control condition; a score >0 at any assessment will trigger a pop up message to be presented to the patient within the mobile app reminding participants that if they are experiencing suicidal thoughts, they should seek professional help or go to the emergency room right away. Links to 988, 911, as well as a national suicide hotline, will be provided within this popup notification. A score >1 will also trigger notification to the clinician/coach via text message or email. In the case that a BA-level coach is notified that a participant reported a score >1 , they will notify a doctoral-level study clinician as soon as possible (and within 24 hours). A study clinician, PI, or independent evaluator will follow up with a phone evaluation within 24 hours of the alert and refer the participant to a higher level of care if clinically indicated. To be able to determine which participant triggered the alert (i.e., to link the de-identified trigger with the actual

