15. The CBT treatment will initially emphasize cognitive restructuring, which we anticipate will be less anxiety provoking than exposure treatment alone and will make exposure more tolerable.
16. Technologists from Koa Health who conduct the technology feedback interviews are highly trained professional staff with experience conducting patient interviews and user-

centered design. They have received additional training (including a multi-day workshop) from our team (The Center for OCD and Related Disorders) on CBT, and issues of confidentiality. They have completed CITI training.

17. Three clinical psychologists or researchers familiar with OCD will be selected to serve as a Data Safety Monitoring Board, to review the study once a year.
18. The subject will designate a relative or friend who could be contacted should the subject be unavailable and the investigator has concerns about the subject's well-being.
19. The digital application will be scanned by Veracode prior to deploying the app to participants.
20. Participants will not be asked to refrain from seeking treatment between the 3-month follow-up assessment and the 12-month follow-up assessment.

We anticipate that the above procedures will be effective in protecting study participants against potential risks.

Adverse event reporting:

See below: "Adverse event reporting guidelines"

E. Radiation risks

Not applicable

VIII. POTENTIAL BENEFITS

A. Potential benefits to participating individuals

Participants may benefit from the comprehensive diagnostic assessment with a clinician assessor. Participants may benefit from careful clinical monitoring and potentially effective treatment. This study has the potential benefit of improving the patients' OCD symptoms.

B. Potential benefits to society

If app-based CBT for OCD is effective, it may offer increased, cost-effective access to CBT for OCD, a treatment that is empirically supported and is otherwise difficult to access.

IX. MONITORING AND QUALITY ASSURANCE

A. Independent monitoring of source data. [name] and employees of Decus Biomedical, Inc. were hired by Koa Health to serve as study monitors. They may conduct visits up to 4 times yearly and will review study data to provide feedback regarding ongoing study procedures as they relate to any potential future pursuit of FDA clearance for the *Perspectives* app.

B. Study staff monitoring of source data

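### The covariate model planned for the exploratory 12-month contrast cannot be relied on to account for outside treatment, because that treatment starts after randomisation and may follow worsening the model does not contain

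*Combined protocol and SAP*

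**What the plan says.** Exploratory endpoint 2 (section VI.C) adds the 3- and 12-month visits to the mixed models and uses contrasts "to test for significant treatment group differences at the 12-month follow-up time-point", for each of Y-BOCS, QIDS-SR, WSAS and Q-LES-Q-SF. For Y-BOCS this tests Hypothesis 4 in section VI.B: "At the 12-month follow-up assessment, participants who received app-CBT will have lower Y-BOCS scores than those in the supportive attentional control condition".

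The sensitivity analysis has a trigger: "In the case that at least 10% of the participants who completed the end-of-treatment assessment initiated additional or subsequent evidence-based treatment for OCD", at a dose or frequency judged clinically meaningful. The model is then refitted "using treatment (yes/no) as a time-varying covariate in the model to account for the potential effect of outside treatment". No other analysis for outside treatment at follow-up is planned, and no estimand is named for the 12-month contrast.

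Other parts of the document bear on that covariate:
- Hypothesis 5 (section VI.B) expects that app-arm participants "will be less likely to seek additional treatment for OCD than participants assigned to the supportive attentional control condition".
- The primary analysis leaves out follow-up visits "because treatment response could be affected by subjects seeking other treatments during the FU period".
- Section VII.D, item 20: "Participants will not be asked to refrain from seeking treatment between the 3-month follow-up assessment and the 12-month follow-up assessment".
- The Measures Chart schedules Y-BOCS at 3 and 12 months, with nothing between.

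**The concern.** Outside treatment is not a baseline characteristic. By the plan's own expectations it can lie on the path from arm to 12-month outcome, so conditioning on it gives up the comparison that randomisation protects. If people who get worse are the ones who seek care, and that worsening falls between the two follow-up visits, the covariate's coefficient mixes the benefit of outside treatment with the severity that led to it. A useful outside treatment can then look inert or harmful.

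What is at stake is how the 12-month result is read. If more control participants are treated elsewhere, the unadjusted difference is smaller than it would have been with no outside treatment. A reader told that the second model accounts for this may take two similar estimates as proof that outside treatment did not matter. The two can agree while both miss that quantity.

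**Working it through.** **The plan's own figure.** Section VI.D gives effect 0.76, SD 1.1, two-sided alpha 0.05, power 0.90 and 20% dropout. With the noncentral t, 46 per arm gives power 0.906. Then 46 / 0.8 = 57.5, rounded up to 58 per arm, 116 in total, as stated. This figure is not in dispute. With 120 randomised, 120 × 0.8 = 96 complete week 12 (48 per arm), and the trigger is 0.10 × 96 = 9.6, so 10 people.

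**How dilution and adjustment work.** Let Δ be the 12-month arm difference had nobody been treated elsewhere, τ the effect of outside treatment, p_A and p_C uptake in the app and control arms, and c the fitted covariate coefficient. When outside treatment starts after the 3-month visit:
- unadjusted ≈ Δ + τ(p_A − p_C)
- adjusted ≈ unadjusted − c(p_A − p_C)
- share of the dilution corrected ≈ c / τ

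The adjustment therefore works only as far as c estimates τ.

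**Simulation on the plan's scale.** From the document: 96 completers, SD 1.1, and 0.76, here taken as the 12-month difference without outside treatment. Assumed, because the document gives no values: within-person correlation 0.6, τ from −0.4 to −0.8, the uptake rates shown and what drives them. Models have an unstructured covariance; 3,000 replicates per row.

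| Driver of uptake | Uptake, control / app | τ | Unadjusted | c | Adjusted | c / τ |
|---|---|---|---|---|---|---|
| Arm only | 16% / 6% | −0.4 | −0.722 | −0.401 | −0.759 | 1.00 |
| Recorded 3-month score | 38% / 25% | −0.4 | −0.707 | −0.403 | −0.762 | 1.01 |
| Arm, 3-month score and unrecorded worsening | 40% / 20% | −0.4 | −0.686 | −0.013 | −0.689 | 0.03 |
| Same | 40% / 20% | −0.6 | −0.636 | −0.219 | −0.680 | 0.37 |
| Same | 40% / 20% | −0.8 | −0.604 | −0.414 | −0.686 | 0.52 |
| Same, low uptake | 13% / 5% | −0.4 | −0.729 | −0.017 | −0.730 | 0.04 |
| Unrecorded worsening only | 38% / 25% | −0.4 | −0.703 | +0.127 | −0.686 | −0.32 |
| Same | 38% / 25% | −0.8 | −0.652 | −0.274 | −0.688 | 0.34 |
| Same, strong | 45% / 27% | −0.4 | −0.688 | +0.308 | −0.634 | −0.77 |

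The formulas reproduce the rows. Third row: −0.76 + (−0.4)(−0.20) = −0.68 unadjusted (simulated −0.686), then −0.686 − (−0.013)(−0.20) = −0.689 adjusted. Last row: −0.688 − (0.308)(−0.18) = −0.633 (simulated −0.634), further from −0.76 than before adjustment.

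Dilution in the table runs from 0.76 − 0.729 = 0.031 (4%) to 0.76 − 0.604 = 0.156 (21%). In the third row the two analyses reach the same significance verdict in 98% of trials, and in the low-uptake row in 99%.

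**Simulation in Y-BOCS points.** Assumed: Δ = −4, τ = −4, SD 7, correlation 0.6, 48 per arm, unrecorded worsening as the driver. The slope is the change in log-odds of uptake per point.
- Slopes 0.05 to 0.15: partial correction, for example −3.72 to −3.84.
- Slope 0.25: −3.62 to −3.54.
- Slope 0.40: −3.38 to −3.07. At slopes 0.25 and 0.40 the coefficient is +0.8 to +2.1 instead of −4.
- Uptake driven only by arm or by the 3-month score: corrected to about −4.0.

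Dilution here is 4 − 3.72 = 0.28, 4 − 3.62 = 0.38 and 4 − 3.38 = 0.62 points, about 0.3 to 0.6 of 4.

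**The case against.** The strongest reply is that the main estimate is already sound. Hypothesis 4 is tested by the unadjusted contrast between randomised arms, which is a valid treatment-policy comparison. The covariate model is a conditional sensitivity analysis of an exploratory endpoint, and the primary model excludes follow-up visits for this very reason. All of that stands. The dilution is also modest and works against the app.

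The evidence about drivers is limited too. Hypothesis 5 is a hypothesis, and it covers any treatment seeking, whereas the covariate counts only evidence-based treatment at a meaningful dose or frequency. The document does not say that worsening drives uptake between months 3 and 12. Its nearest statement is in section VII.D, item 5, where deterioration on weekly ratings leads a clinician to "refer the participant to a higher level of care if clinically indicated"; those ratings are not terms in the model. This stands, and it makes the failure conditional.

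A reader might infer more than the document supports:
- That the adjustment always fails, or succeeds only if uptake depends on the recorded 3-month score alone. It also succeeds when uptake depends only on arm, and it corrects part of the dilution when severity-driven seeking is weak or the outside effect is large.
- That the plan commits to calling an unchanged estimate robust. It contains no such rule. The risk comes from the purpose it gives the model.
- That the covariate model should be replaced by a responder composite. The composite covers only Y-BOCS, does not estimate the effect without outside treatment, and combines Hypotheses 4 and 5. In a simulation with no Y-BOCS effect, an inert outside treatment and uptake of 27% against 15%, it still favoured the app by about 5 percentage points.

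**Conclusion.** The point holds in conditional form. The planned model conditions on a post-randomisation variable, and the claim that it accounts for outside treatment is stronger than the design supports. Whether it corrects the dilution depends on why people start treatment. In the scenarios checked, the share corrected ran from all of it, through about half or a third, to none, and in some the dilution grew. Failure requires severity-driven uptake that the recorded visits do not capture; the gap between the 3- and 12-month visits makes that plausible but does not establish it.

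Size and direction rest on assumed uptake, outside-treatment effect and strength of severity-driven seeking, none of which the document gives. The dilution counts as distortion only if the target is the effect without outside treatment. Neither the validity of the unadjusted 12-month contrast as a treatment-policy estimate, nor the week-12 primary result, nor the sample size of 116 is in question. The change is worth making because it governs what may be concluded when the two 12-month estimates agree.

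**What to change.** In section VI.C, Exploratory endpoint 2:
1. State that the unadjusted 12-month contrast is the treatment-policy estimate: the arm difference whatever treatment followed.
2. Strike the clause that gives the covariate model its purpose, and label that model associational for all four outcomes.
3. State that agreement between the adjusted and unadjusted results is not evidence of robustness to outside treatment.
4. As a supplement, report by randomised arm the proportion who are Y-BOCS responders at 12 months (the plan's 25% rule) without having started outside evidence-based OCD treatment, with a confidence interval for the difference. Handle missing 12-month scores as the plan already does for week-12 response: as observed, last observation carried forward, and missing as non-response. Describe it as response without outside treatment, not as maintenance, because it includes people who first respond after week 12.
5. Edit the sentence that rules out formal comparison of responder counts so that it matches item 4.

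The cost is SAP wording and one extra table. The 12-month Y-BOCS and the concomitant medication and therapy log are already collected. The composite is binary, less precise than a mean difference, limited to Y-BOCS, and mixes symptom benefit with treatment seeking, so it must be read beside the separate results for Hypotheses 4 and 5.
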